8.2.2 Subpopulations

Subgroup analyses will be performed on primary, secondary and tertiary efficacy endpoints as defined in section 14. All subgroup analyses will be exploratory and descriptive in nature.

In case of low number of participants within a category (< 25% participants by subgroup categories), subgroup analysis for that variable will not be performed.

Subgroups analyzed are:

1. Subgroup Treatment Course in Cohort B
2. Long-term Responder/Non-responder (4 definitions)
3. Subset Types of Subsequent DMDs
4. Subgroup Prior Use of DMD for cohort B
5. Subgroup HDA for Cohort B

It should be noted that the subgroup analyses on the subgroups' treatment courses and subsequent DMD do not support the comparison of any treatment effect as the definition of subgroups already is not independent from randomized treatment.

1. Subgroup Treatment Course in Cohort B:

- a) **Placebo:** Study participants who received placebo only (i.e. study participants that received placebo in CLARITY who did not enter CLARITY-EXT, or received placebo in both CLARITY and CLARITY-EXT)
- b) **1 treatment course (year) of Cladribine:** Study participants who received at least 1 dose of Cladribine Tablets during either CLARITY or CLARITY -EXT but did not start the 2nd year treatment courses of Cladribine Tablet.
- c) **2 treatment courses (years) of Cladribine:** Study participants who received at least 1 dose of Cladribine Tablets during either CLARITY or CLARITY -EXT that started the 2nd year treatment courses of Cladribine Tablets but did not started a third-year treatment course of Cladribine treatment.
- d) **More than 2 treatment courses (years) of Cladribine:** Study participants who received at least 1 dose of Cladribine Tablets during CLARITY and CLARITY -EXT that started > 2 treatment courses of Cladribine Tablets (i.e. patients who completed CLARITY and started at least the 1st year treatment courses in CLARITY-EXT). This corresponds to participants who completed 2 courses of Cladribine treatment and started the third course of Cladribine treatment.

Computation rules:

The above groups will be determined based on how many treatments years participant had in the parent study:

Year 1: From first Cladribine dose date to End of Year 1.

End of Year 1 is defined as the day of the earliest exposure greater or equal to year 1 start date + 308 days

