To define (b), (c) and (d): If at least 1 dose of Cladribine has been administered after end of Year 1, for CLARITY or CLARITY EXT then the participant will be considered starting the second treatment course (year). If at least 1 dose of Cladribine has been administered during the first year of CLARITY EXT after receiving at least 1 dose during the second treatment course of CLARITY, then the participant will be considered starting the third treatment course (year). Individual parent study datasets will be used.

2. Long-term Responder/Non-responder:

a. Primary definition

- **Long-term Responder:** Study participants not requiring DMD 4 years or later following their last dose of IMP, and who did not demonstrate any evidence of disease reactivation based on Investigator assessment of clinical and imaging outcomes
- **Non-Responder:** Study participants requiring DMD less than 4 years following their last dose of IMP or who demonstrate any evidence of disease reactivation based on Investigator assessment of clinical and imaging outcomes.

Computation rules:

Prior/concomitant medication eCRF page and “physician sequential treatment decision questions” eCRF page question 8 and 9 to be used to identify the date of the DMD received.

4 years after last dose of IMP = Last dose of IMP date + 4*365.25 days

Evidence of disease reactivation will be defined by either:

- a) MRI lesions: new T1 lesion or new T2 lesion reported
- b) New Relapse reported
- c) EDSS worsening defined as an EDSS score increase of at least 1 point between 2 consecutive visits of at most 365 days (if 2 consecutive EDSS assessments are separated by more than 365 days then EDSS cannot be used in the criteria and will be considered as missing/not reported).

New relapse, MRI lesions and EDSS worsening will be identified utilizing dates in parent studies for the period between last dose of IMP and end of parent study.

For the period following the end of the parent study until SV1 of Classic study the following source data will be used:

- 1) MRI lesion by the eCRF “frequency stable patient monitoring questions” (fspmq) page,

Q4/Q3. If Q4 is answered “yes” the date will be taken from Q3 and determined if the MRI lesion is before the 4 years since last IMP.

- 2) New relapse will be identified using the eCRF “MS Relapse history” page(hxrelap) Q2.2.
- 3) The EDSS worsening by the eCRF “expanded disability status scale (edssr) for retro data” page.

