14.2 Secondary Endpoint

14.2.1 Long-term disability status

The secondary efficacy endpoint of this study will be evaluated descriptively by percentage and 95% CI of patients with EDSS of 6.0 or higher since last dose of IMP until Visit 1. The results of the confidence scale of EDSS values will be presented descriptively for worst EDSS score (available only for Retro EDSS). The worst EDSS value will be summarized by categories for each cohort.

EDSS will be assessed clinically (on site) and by phone.

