Table 15.2.1.4.4	Proportion of patients using a wheelchair (EDSS>=7) the majority of the time in the 3 months prior to Study Visit 1 or bedridden – Cohort D- FAS analysis set- Subset Long-term Responder (Sensitivity Def B)		
Table 15.2.1.4.5	Proportion of patients using a wheelchair (EDSS>=7) the majority of the time in the 3 months prior to Study Visit 1 or bedridden – Cohort D- FAS analysis set- Subset Long-term Responder (Sensitivity Def C)		
Figure 15.2.1.1.1	Forest Plot of Proportion of patients using a wheelchair (EDSS>=7) the majority of the time in the 3 months prior to Study Visit 1 or bedridden- Cohort A- FAS analysis set		
15.2.2: Secondary Endpoint 1			

Table 15.2.2.1.1	Proportion of patients with EDSS of 6.0 or higher since last dose of IMP – Cohort A- FAS analysis set	Y	U
Table 15.2.2.1.2	Proportion of patients with EDSS of 6.0 or higher since last dose of IMP– Cohort A- FAS analysis set- Subset Long-term Responder		
Table 15.2.2.1.3	Proportion of patients with EDSS of 6.0 or higher since last dose of IMP– Cohort A- FAS analysis set- Subset Types of Subsequent DMDs		
Table 15.2.2.1.4	Proportion of patients with EDSS of 6.0 or higher since last dose of IMP– Cohort A- FAS analysis set- Subset Long-term Responder (Sensitivity Def B)		
Table 15.2.2.1.5	Proportion of patients with EDSS of 6.0 or higher since last dose of IMP– Cohort A- FAS analysis set- Subset Long-term Responder (Sensitivity Def C)		
Table 15.2.2.2.1	Proportion of patients with EDSS of 6.0 or higher since last dose of IMP – Cohort B- FAS analysis set		
Table 15.2.2.2.2	Proportion of patients with EDSS of 6.0 or higher since last dose of IMP – Cohort B- FAS analysis set- Subgroup Treatment Course		
Table 15.2.2.2.3	Proportion of patients with EDSS of 6.0 or higher since last dose of IMP – Cohort B- FAS analysis set- Subset Long-term Responder		
Table 15.2.2.2.4	Proportion of patients with EDSS of 6.0 or higher since last dose of IMP – Cohort B- FAS analysis set- Subset Types of Subsequent DMDs		
Table 15.2.2.2.5	Proportion of patients with EDSS of 6.0 or higher since last dose of IMP – Cohort B- FAS analysis set- Subgroup Prior Use of DMDs		
Table 15.2.2.2.6	Proportion of patients with EDSS of 6.0 or higher since last dose of IMP – Cohort B- FAS analysis set- Subgroup HDA		
Table 15.2.2.2.7	Proportion of patients with EDSS of 6.0 or higher since last dose of IMP– Cohort B- FAS analysis set- Subset Long-term Responder (Sensitivity Def B)		

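### In the EDSS 6.0 tables by responder subset, one EDSS rise can make a patient a non-responder and also be the outcome event, which tilts the contrast towards responders

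*SAP*

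**What the plan says.** **Classifier.** SAP 8.2.2 builds the primary responder definition (A) from four components: DMD use, new MRI lesion, new relapse and EDSS worsening. One positive component is enough for non-response. The EDSS component is "EDSS worsening defined as an EDSS score increase of at least 1 point between 2 consecutive visits of at most 365 days". Definition C drops the DMD component and keeps EDSS. Definition B uses DMD only. Definition D (clinical outcomes only) also keeps EDSS, but SAP 17.1 lists no table for it.

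**Window.** The rules set "4 years after last dose of IMP = Last dose of IMP date + 4*365.25 days". For reactivation after the parent study they apply that limit explicitly only to imaging: it is to be "determined if the MRI lesion is before the 4 years since last IMP". The general statement is "For the period following the end of the parent study until SV1 of Classic study the following source data will be used", with no cut-off given for relapse or EDSS. The endpoint definition in SAP section 5 and Protocol section 3 does limit reactivation to the period before Year 4.

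**Outcomes.** The secondary endpoint counts "patients with EDSS of 6.0 or higher since last dose of IMP until Visit 1" (SAP 14.2.1). The primary endpoint (SAP 14.1) has parts with different periods. EDSS of at least 7 is read in the 3 months before Study Visit 1 (SV1) or at SV1. EDSS of at least 8 is read at any time after first dose. MS deaths are included with no stated time limit.

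**Outputs.** SAP 17.1 lists both endpoints by responder subset ("FAS analysis set- Subset Long-term Responder") in Cohorts A to D. No title mentions a landmark or excludes patients already at the milestone.

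**Caution.** SAP 8.2.2 and Protocol 9.3 warn that analyses by "treatment courses and subsequent DMD do not support the comparison of any treatment effect". Responder status is not mentioned.

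**The concern.** Response is judged over a period after last dose, and the EDSS 6.0 endpoint starts counting on the same day. A patient who moves from 5.0 to 6.0 at consecutive visits in Year 2 becomes a non-responder because of that record, and the same record is the outcome event. Non-responders therefore collect early events that the definition tends to remove from responders. Some difference would appear even if response carried no information about later disability.

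At stake is how the tables are read. They are descriptive, so no test is invalidated. But the protocol says that the study may inform treatment decisions, and a table with fewer disabled patients among responders is easily taken as evidence that early response predicts long-term mobility.

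**Working it through.** **Which tables are affected (SAP 17.1).** Each endpoint has 3 responder definitions (A, B, C) × 4 cohorts = 12 tables, so 24 in all.

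| Definitions | EDSS 6.0 tables | Primary-endpoint tables |
|---|---|---|
| A and C (EDSS in the classifier) | 8 | 8 |
| B (DMD only) | 4 | 4 |

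**The plan's own figure.** The documents give no number for the responder contrast. The only planning figures are the confidence-interval half-widths in Protocol 9.2. They follow from 1.96·√(p(1−p)/n)·√((N−n)/(N−1)) with N = 1,958. For n = 587 and p = 5% this gives 1.48%, as printed. They do not bear on this point.

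**Is the wheelchair look-back inside the window?** The longest span from first to last dose that SAP 6.2 implies for CLARITY/CLARITY-EXT is 96 + 118 + 53 = 267 weeks, or 5.1 years (53 = second-year dosing in Week 5). With SV1 about 10 years after first treatment (Protocol section 9), the 3-month look-back starts about 10 − 5.1 − 0.25 = 4.6 years or more after last dose. That is outside a 4-year window.

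**EDSS 6.0 when response predicts nothing.** All inputs here are assumptions:
- q = cumulative risk of EDSS 6.0 by SV1, at a constant hazard equal for everyone (10%, 20%, 30%)
- T = years from last dose to SV1 (5, 8, 11)
- r = probability of non-response for unrelated reasons (0.5 unless stated)
- f = share of crossings in the first 4 years that the 1-point rule flags

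Formulas:
- share crossing in the window: w = 1 − (1 − q)^(4/T)
- responder risk: (q − fw)/(1 − fw)
- non-responder risk: [q − (1 − r)(q − fw)]/[1 − (1 − r)(1 − fw)]

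For q = 20%, T = 8, r = 0.5: w = 1 − 0.8^0.5 = 10.6%.

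| f | Responders | Non-responders | Ratio |
|---|---|---|---|
| 0 | 20.0% | 20.0% | 1.00 |
| 0.25 | 17.8% | 22.1% | 1.24 |
| 0.5 | 15.5% | 24.0% | 1.54 |
| 1 | 10.6% | 27.6% | 2.62 |

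At f = 0.5, the ratio runs from 1.34 (q = 30%, T = 11) to 2.17 (q = 10%, T = 5). At f = 1 the same grid runs from 1.85 to 8.0, with the top at q = 10%, T = 5.

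**A patient-level simulation** (also assumptions: 600,000 patients, 9.5 years after last dose, memoryless one-point rises at 0.08 to 0.18 per year, starting EDSS about N(3, 1.2) and at most 5.5, no other cause of non-response) gives 4.0 v 19.9%, 6.9 v 27.5% and 12.0 v 39.2%, ratios 5.0, 4.0 and 3.3. Adding unrelated non-response in 30 to 70% of patients lowers the ratio to 2.3 to 3.2. With 50% unrelated non-response and half of the progression in unflagged half-point steps, it is about 1.7 to 1.8; with three quarters, about 1.4.

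**Primary endpoint** (total 10%, T = 8, r = 0.5, f = 0.5). If only bedridden or MS-death events in the window create the link, the result is 9.8 v 10.2% when they make up 10% of events (ratio 1.05) and 8.9 v 11.1% when they make up 50% (1.26). If an EDSS of 7 reached in the window persists to SV1, it is 7.6 v 12.3% (1.61).

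**If the EDSS criterion really ran to SV1**, w becomes q. With q = 20% and r = f = 0.5, responders have (0.20 − 0.10)/0.90 = 11.1%, non-responders (0.20 − 0.05)/0.55 = 27.3%, ratio 2.45. A Year-4 landmark could not repair that.

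**After the fix.** With patients below the milestone at 4 years and later events only, both groups have 1 − (1 − q)^((T−4)/T) = 1 − 0.8^0.5 = 10.6%.

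**The case against.** Several stronger readings are tempting, and the documents do not support them.

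- *Responders must look better because their first 4 years are outcome-free.* The rule flags a jump of at least 1 point within 365 days, not a level. A step from 5.5 to 6.0 is not flagged, and a patient already at 6.0 at last dose counts as an event yet can be a responder. Suppose 10% are already at 6.0 and only 20% of them are flagged, with q = 20%, T = 8, r = f = 0.5 for the rest. Responders then have 28.9% and non-responders 27.1%. The bias is expected, not guaranteed.
- *The wheelchair endpoint counts any EDSS of 7 since first dose.* SAP 14.1 reads that score only near SV1. Only EDSS of at least 8 runs from first dose.
- *All 24 tables share the scale.* Definition B has no EDSS in its classifier, and its tables offer a partial check.
- *Most of the contrast is definitional, with a ratio of 3 to 5.* That needs EDSS as the sole cause of non-response and whole-point rises only. In the same type of model a landmark alone still leaves ratios of 1.4 to 2.8, because patients who worsened start Year 4 closer to 6.0. That part is real prediction through EDSS level. Standardising on EDSS at Year 4 brings the ratio to about 1.0, but it answers a different question.

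It is also fair that the subgroup analyses are labelled exploratory and descriptive, that component-level summaries are planned, and that the printed caution concerns independence from randomized treatment, so its silence on responders is not an inconsistency. None of this removes the overlap in the EDSS 6.0 tables under Definitions A and C: a descriptive label does not tell the reader that classifier and outcome can be the same record.

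**Conclusion.** The point holds for the 8 EDSS 6.0 tables under Definitions A and C, where period and scale both overlap. It holds in weaker form for the 8 matching primary-endpoint tables: directly through early bedridden or MS-death events, indirectly through disability that persists to SV1. The 8 Definition B tables share only the period.

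The expected direction favours responders. The size rests on f, r, T and the cumulative rate, none of which the documents give. For EDSS 6.0 a reasonable range is about 1.3 to 2.2 with half of early crossings flagged; it is 1.0 with none flagged. Values of 3 to 5, or higher with short follow-up, need every crossing flagged.

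A reader might also infer from SAP 8.2.2 that relapse and EDSS worsening count against response right up to SV1. The text leaves this open, and the endpoint definition in SAP section 5 points to a Year 4 limit. It needs settling, because the landmark works only if classification closes at that date. The harm is misreading of descriptive tables, not a false test result.

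**What to change.** 1. In SAP 8.2.2, apply the limit of last dose + 4*365.25 days to relapse and EDSS worsening as well as MRI lesions, in line with the endpoint definition.
2. For the responder-subset tables of the EDSS 6.0 endpoint, and for the bedridden and MS-death part of the primary endpoint, add a landmark version. Include only patients alive, observed and below the milestone at last dose + 4 years, and count only later events. Standardisation on the last available EDSS before the landmark can be an optional sensitivity analysis where that score is recorded. No Year-4 visit is scheduled, and SAP 8.2.2 itself expects retrospective EDSS to be missing, so it cannot be the main analysis.
3. Extend the caution in SAP 8.2.2 and Protocol 9.3: responder status is not independent of the disability outcomes, and these tables do not show that response predicts later mobility.

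The cost is SAP wording, a short protocol clarification, and extra programming for the landmark tables. Those tables will have fewer patients and events, and patients not observed at Year 4 drop out of them. The planned tables can stay, with the caution attached.

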8.1.1 Clinical Endpoints

8.1.1.1 Expanded Disability Status Scale (EDSS)

The EDSS is a neurological assessment that will be used to assess the long-term disability progression following treatment with IMP in the parent studies (Appendix 5 Expanded Disability Status Scale (EDSS)). EDSS is a scale from 0-10 that evaluates a person with MS's disability/neurologic function level with 6 being the critical point at which a patient requires ambulatory assistance. The primary endpoint of proportion of study participants using a wheelchair (defined as unable to walk beyond approximately 5 meters even with aid,

essentially restricted to wheelchair; wheels self in standard wheelchair and transfers alone; up and about in wheelchair some 12 hours a day) the majority of the time in the 3 months prior to Study Visit 1 or participants are bedridden any time prior to Study Visit 1 determined via an EDSS score of 7.0 or higher (if available), or alternative clinical description data in medical records. The secondary endpoint will be determined as the proportion of study participants with EDSS of 6.0 or higher by EDSS documentation or alternative clinical description in medical records after last IMP from parent study.

Sustained disease progression is important because transient increases in the EDSS may also be due to relapses, which reflect disease activity rather than disease progression (Healy, 2013); an EDSS measurement taken at a single point in time may be subject to measurement error (Goodkin, 1992). As such, confirmation of sustained EDSS score is needed to mitigate against measurement error and EDSS fluctuation (Kalincik, 2015).

Furthermore, while EDSS scores at any timepoint, regardless of their relationship to relapses, may serve as evidence of EDSS progression, it is generally recommended that only EDSS scores that are recorded more than 30 days from the onset of a preceding relapse be used in order to confirm progression events (Kalincik, 2015). As such, Investigators in this study will be instructed to exclude any EDSS score recorded within 30 days of a previous relapse.

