Appendix 5 Expanded Disability Status Scale (EDSS)

General

- The Evaluating Physician will complete the Expanded Disability Status Scale (EDSS).
- The same individual should remain as the Evaluating Physician for each patient, except when exceptional circumstances make this impossible.
- Prior to each neurological assessment, the Evaluating Physician **should not** refer to any previous neurological assessments carried out on that patient.
- The current EDSS will be recorded (i.e. the EDSS as assessed during the visit).

EDSS SCORING

- **0.0** Normal neurological exam [all grade 0 in all Functional System (FS) scores*]
- **1.0** No disability, minimal signs in one FS* (i.e., grade 1)
- **1.5** No disability, minimal signs in more than one FS* (more than 1 FS grade 1)
- **2.0** Minimal disability in one FS (one FS grade 2, others 0 or 1)
- **2.5** Minimal disability in 2 FS (2 FS grade 2, others 0 or 1)
- **3.0** Moderate disability in one FS (one FS grade 3, others 0 or 1) or mild disability in 3 or 4 FS (3 or 4 FS grade 2, others 0 or 1) though fully ambulatory
- **3.5** Fully ambulatory but with moderate disability in one FS (one grade 3) and one or 2 FS grade 2; or 2 FS grade 3 (others 0 or 1) or 5 grade 2 (others 0 or 1)
- **4.0** Fully ambulatory without aid, self-sufficient, up and about some 12 hours a day despite relatively severe disability consisting of one FS grade 4 (others 0 or 1), or combination of lesser grades exceeding limits of previous steps; able to walk without aid or rest some 500 meters
- **4.5** Fully ambulatory without aid, up and about much of the day, able to work a full day, may otherwise have some limitation of full activity or require minimal assistance; characterized by relatively severe disability usually consisting of one FS grade 4 (others 0 or 1) or combinations of lesser grades exceeding limits of previous steps; able to walk without aid or rest some 300 meters
- **5.0** Ambulatory without aid or rest for about 200 meters; disability severe enough to impair full daily activities (e.g., to work a full day without special provisions); (Usual FS equivalents are one grade 5 alone, others 0 or 1; or combinations of lesser grades usually exceeding specifications for step 4.0)
- **5.5** Ambulatory without aid for about 100 meters; disability severe enough to preclude full daily activities; (Usual FS equivalents are one grade 5 alone, others 0 or 1; or combination of lesser grades usually exceeding those for step 4.0)

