All partial dates will be imputed as described in Section 9.5.

Different scenarios considering missing/not collected data are provided in the table below:

DMD required	MRI new lesion	New Relapse	EDSS worsening	Responder (Yes/No/ND)
All are missing				ND
At least one is Yes (with or without missing)				No
All are N (with no missing)				Yes
All are N (with at least one missing)				ND

ND=Not determined

b. Definition B (sensitivity):

- **Long-term Responder:** Study participants not requiring DMD 4 years or later following their last dose of IMP.
- **Non-Responder:** Study participants requiring DMD less than 4 years following their last dose of IMP.

c. Definition C (sensitivity)

- **Long-term Responder:** Study participants who did not demonstrate any evidence of disease reactivation based on Investigator assessment of clinical and imaging outcomes 4 years following the last dose of IMP.
- **Non-Responder:** Study participants who demonstrate any evidence of disease reactivation based on Investigator assessment of clinical and imaging outcomes 4 years following the last dose of IMP.

d. Definition D (sensitivity)

- **Long-term Responder:** Study participants who did not demonstrate any evidence of disease reactivation based on Investigator assessment of clinical outcomes 4 years following the last dose of IMP.

- **Non-Responder:** Study participants who demonstrate any evidence of disease reactivation based on Investigator assessment of clinical outcomes 4 years following the last dose of IMP.

Definition A described above is considered the primary definition and will be used in the final analysis. Definition B (definition A revised, using DMD only), Definition C (definition A revised, using reactivation of disease only), and Definition D (as C but removing MRI criteria) will be also performed as a sensitivity analysis. MRI lesions or retro EDSS information are expected to be missing/not collected/not reported. Additional descriptive statistics will be provided for each of the component used in the definition to assess the validity of the criteria.

3. Subset Types of Subsequent DMDs:

- Platform injectable therapy (Interferon- β [Avonex[®], Rebif[®], Betaferon[®], Extavia[®], Plegridy[®]] or glatiramer acetate [Copaxone[®]])
- Monoclonal antibody disease modifying treatment
- Oral disease modifying treatment
- Other subsequent treatment
- Off-label treatments (drugs not approved by regulatory agencies to treat MS)
- No subsequent treatment

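### The EDSS part of the responder definition counts any single one-point rise between neighbouring visits, with no fixed reference and no confirmation, so it depends on visit spacing and single-score error.

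*SAP*

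**What the plan says.** SAP 8.2.2, primary definition of long-term responder, gives three signs of disease reactivation. The third is "EDSS worsening defined as an EDSS score increase of at least 1 point between 2 consecutive visits of at most 365 days". It adds a limit on spacing: "if 2 consecutive EDSS assessments are separated by more than 365 days then EDSS cannot be used in the criteria", and such an assessment is then treated as missing. For the period after the parent study the source is chart data: "The EDSS worsening by the eCRF “expanded disability status scale (edssr) for retro data” page".

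The scenario table in the same section gives each component full weight. The row "At least one is Yes (with or without missing" leads to Non-Responder. If every component is No but at least one is missing, the result is not determined.

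Sensitivity Definitions C and D keep the EDSS rule (D drops MRI only). Definition B uses DMD alone.

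Protocol 8.1.1.1 cautions that "an EDSS measurement taken at a single point in time may be subject to measurement error" and says that "confirmation of sustained EDSS score is needed to mitigate against measurement error and EDSS fluctuation". It also states that "Investigators in this study will be instructed to exclude any EDSS score recorded within 30 days of a previous relapse".

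**The concern.** The rule compares each score with the one just before it, not with the level at last dose. EDSS moves in half points over this range: the protocol's Appendix 5 places a 2.5 level, "Minimal disability in 2 FS (2 FS grade 2, others 0 or 1", between 2.0 and 3.0. A patient can therefore lose several half points at successive visits without any neighbouring pair differing by 1.0. In the other direction, one high (or one low) reading is enough to create a one-point rise, and each further visit gives another chance of that.

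After the parent study the scores come from chart review, so the number and spacing of visits will differ between patients. The component would then partly measure how often someone was examined.

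The responder flag is used for two secondary endpoints (SAP 14.2.2 and 14.2.3), the HDA comparison (14.3.5), the genetic association (14.3.6), and the responder subgroup tables for the primary and first secondary endpoints (Appendix 17.1).

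**Working it through.** The documents give no figure for the behaviour of this rule, so there is none to reproduce.

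**Rules compared**
- SAP rule: worsening if any x(j+1) − x(j) ≥ 1.0, with the two visits at most 365 days apart.
- Confirmed rule: worsening if x(j) − x(ref) ≥ 1.0 and x(j+1) − x(ref) ≥ 1.0, where x(ref) is the first score in the series.

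**Fixed score paths, 6-monthly visits (no assumption about error)**

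| Scores | Total change | Largest consecutive rise | SAP rule | Confirmed rule |
|---|---|---|---|---|
| 2.0, 2.5, 3.0, 3.5, 4.0 | +2.0 | 0.5 | no worsening | worsening |
| 2, 2, 3, 2, 2 | 0 | 1.0 | worsening | no worsening |

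If DMD, relapse and MRI are all No and none is missing, the first patient is a Responder. The second is a Non-Responder whatever the other components show.

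**Role of the 365-day limit.** If the five scores of the first path were spread over four full years, the four gaps would total 4 × 365.25 = 1,461 days, but four gaps of at most 365 days cover only 4 × 365 = 1,460. At least one gap would then exceed the limit. If one such gap makes the component missing, that patient is not determined, provided the other components are No. The blind spot therefore applies to visits no more than 365 days apart.

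**Simulation.** The assumptions, none of them from the documents, are: true EDSS within 0.25 of 3.0 at the start; independent normal error at each visit; scores rounded to the nearest 0.5; every pair within the 365-day limit; 200,000 patients per scenario. The SD of a difference between two scores before rounding is √2 × SD: √2 × 0.25 = 0.35, √2 × 0.35 = 0.49, √2 × 0.5 = 0.71.

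Truly stable patients flagged as worsening:

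| Error SD | SAP rule, 4 pairs | SAP rule, 8 pairs | Confirmed, 4 pairs | Confirmed, 8 pairs |
|---|---|---|---|---|
| 0.25 | 10% | 19% | 1% | 2% |
| 0.35 | 28% | 48% | 5% | 8% |
| 0.5 | 52% | 78% | 11% | 18% |

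Patients with a true steady rise of 2.0 points flagged as worsening:

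| Error SD | SAP rule, 4 pairs | SAP rule, 8 pairs | Confirmed, 4 pairs | Confirmed, 8 pairs |
|---|---|---|---|---|
| 0.25 | 80% | 59% | 98% | >99% |
| 0.35 | 88% | 83% | 93% | 98% |
| 0.5 | 93% | 95% | 84% | 93% |

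Starting every patient at exactly 3.0 changes little. The largest shift is 80% to 75% (SAP rule, decliners, SD 0.25, 4 pairs); 19% becomes 20% and 84% becomes 85%. In the simulation a rise at the last visit cannot be confirmed and is not flagged.

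**The case against.** Four objections carry weight.

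- **Purpose of the rule.** Protocol 8.1.1.1 asks for confirmation when the target is sustained progression, and says that transient rises may reflect relapse activity. SAP item (c) is meant to mark reactivation. A quick rise between close visits is a defensible marker of that, and slow decline is covered elsewhere (SPMS conversion, EDSS of 6.0 or more, worst EDSS). A reader might infer that the SAP contradicts the protocol; the documents do not support that. What remains is the protocol's general warning about error in single scores, which applies to any rule that rests on one reading.
- **Steady decline.** A reader might infer that steady decline never counts. That is exact only for recorded half-point steps. Once error is added, 83–95% of patients with a true 2.0-point rise are flagged at SD 0.35 to 0.5, many of them by noise. DMD, relapse or MRI can also classify such a patient.
- **Assumed error.** The SDs are assumed, and independent errors ignore some safeguards: the same evaluating physician and the required functional-system change (Appendix 5), and the 30-day relapse exclusion. These would lower the false-flag rates. The documents do not say that routine chart scores were recorded under the Appendix 5 conditions, and the 30-day exclusion does not address rater or chart error.
- **Existing checks.** Definition B removes EDSS, the SAP plans descriptive statistics for each component, the EDSS Confidence Scale is reported, and all responder comparisons are descriptive. None of these applies a confirmed or cumulative EDSS change; the component summaries would tabulate the same rule.

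**Conclusion.** The concern holds as a weakness in a classification rule. The two fixed paths follow from the SAP wording alone. The percentages rest on the assumed error SDs, independence and visit spacing, and show direction and rough size: about 10–52% (four pairs) and 19–78% (eight pairs) of stable patients flagged, against 1–11% and 2–18% with a fixed reference and confirmation. The rise in false flags with the number of visits appears at every SD tried.

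The gain is not uniform. At SD 0.5 the confirmed rule detects 84–85% of true decliners against 93% over four pairs, and 93% against 95% over eight.

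The point does not touch the primary endpoint's own definition, and no hypothesis is tested. It is a worthwhile, inexpensive improvement to a flag that two secondary endpoints and the HDA and genetic analyses depend on.

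**What to change.** In SAP 8.2.2 (c), define EDSS worsening as a score at least 1 point above a fixed reference, the last EDSS at or before the last IMP dose, with onset within 4 years of that dose, and confirmed at the next available assessment within a maximum interval stated in advance. The interval needs an upper limit: with none, a score at Study Visit 1, around 10 years after initial treatment, could confirm a noisy early rise through unrelated later decline. Code a rise with no confirming score in the interval as not determined.

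Report the present consecutive-visit rule alongside as a sensitivity definition. If the sponsor prefers to keep it as primary, the minimum is to add the confirmed fixed-reference rule as a further sensitivity definition.

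The cost is SAP wording and programming, with no new data. The drawbacks are somewhat more participants coded not determined, since the SAP already expects gaps in retrospective EDSS, and a small loss of sensitivity if EDSS error is large. The reference is itself a single score, so an unusually low one would carry into every later comparison.
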